The proposed pilot study will query women with ovarian cancer about their preferences for the possible effects of treatments on (1) progression-free survival, (2) overall survival, (3) development of severe side effects, (4) overall quality of life, and (5) ovarian-cancer specific health symptoms. This study will allow us to determine the feasibility of assigning patient-determined weights to different individual endpoints for the future construction of a patient-centered composite endpoint. Because preferences are often sensitive to the method of elicitation, multiple methods of elicitation will be used to assess the robustness of preferences. Baseline quality of life and symptom index elicitation will allow examination of subjects' preferences in relation to their current symptoms and well being.

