Secondary Aim 3 is to estimate the distribution of PFS and overall survival (OS). PFS was defined above. OS is defined as the length of the interval from on-study to death due to any cause. Both PFS and OS will be estimated with the Kaplan-Meier curve. In addition, we will compare the PFS of patients who had prior bevacizumab resistance with that of patients who had prior bevacizumab and chemotherapy resistance. Specifically, within each of these two groups, we will describe PFS with a Kaplan-Meier curve and the 6-month PFS rate (with its 80% confidence interval). We expect the latter group to have worse PFS than the former.

Secondary Aim 4 is to elicit patient preferences for outcomes of ovarian cancer treatment. The distribution of rank preferences for each general attribute will be described using mean ranks as well as the proportions of times each concept was ranked as most

important, second most important, third most important, fourth most important, and least important. In the token ranking exercise, to describe the allocations of tokens across the general attributes, we will report means, standard deviations, and median numbers of tokens for each attribute. To examine consistency between token allocations with rank preferences, we will reverse order the rank preferences such that higher ranks correspond to higher preferences and compute correlation coefficients. We will test whether correlations between ranks and token counts differ between attributes using Spearman rank tests. We will also examine the proportion of patients who provided the highest token counts to their most preferred attribute and vice versa. In the ratings exercise, to describe respondents' ratings on the 5-point Likert scale representing level of concern with each attribute included in the DCE, we will report frequencies of ratings for each attribute as well as means to provide a summary measure.

Secondary Aim 5 is to characterize baseline quality of life and cancer-related symptoms. We will use descriptive characteristics to summarize baseline characteristics for the study cohort enrolled at Duke. These characteristics will include summary scores from the NFOSI-18 and the FACT-GOG-Ntx. We will report means, medians, and standard deviations for continuous variables and counts and proportions for categorical variables.

Statistical Analysis of Translation Research Objectives

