Appendix XI

Rank Preferences and Relative Concern Exercises

When researchers are testing new treatments for ovarian cancer, they have to decide ahead of time what kind of results they want to measure. We would like to find out what kind of results patients think are most important. Some of the outcomes researchers measure are listed below, with descriptions of what they mean.

Overall quality of life. This means how you are doing overall. It includes your physical and emotional well-being and how well you can perform your normal daily activities.

Side effects from treatment. This means health effects that are caused by your cancer treatment. Examples of common side effects of cancer treatment are hair loss, neuropathy or numbness or tingling in your fingers and toes, nausea and vomiting.

Symptoms from cancer. Some common symptoms of ovarian cancer are abdominal fullness, pain or bloating, constipation, loss of appetite, and nausea.

Progression-free survival. This is the average length of time that a woman will spend without any sign of her cancer growing or coming back once she starts a new treatment.

Overall survival. This is the average length of time that a woman will live after starting a new treatment.

A. Relative Concern Exercise

Now please indicate below how concerned you are about each of the following outcomes of your treatment.

Quality of life	Not concerned	A little bit concerned	Moderately concerned	Very concerned	Deeply concerned
Symptoms of cancer	Not concerned	A little bit concerned	Moderately concerned	Very concerned	Deeply concerned
Side effects of treatment	Not concerned	A little bit concerned	Moderately concerned	Very concerned	Deeply concerned
Progression-free survival	Not concerned	A little bit concerned	Moderately concerned	Very concerned	Deeply concerned
Overall survival	Not concerned	A little bit concerned	Moderately concerned	Very concerned	Deeply concerned

B. Rank Preferences

Please rank the following outcomes we can measure in order from the MOST important (1) to the LEAST important (5) to you.

_____ Overall quality of life. This includes your physical and emotional well-being and how well you can perform your normal daily activities.

_____ Side effects that are caused by the treatment.

_____ Symptoms that are caused by ovarian cancer.

_____ Length of time spent without the cancer growing.

_____ Total length of life remaining.

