(To avoid any potential bias introduced associated with the order the concepts are listed, the order will be randomized across participants.)

C. Token distribution exercise

Now imagine that you have 100 coins or tokens. We would like you to distribute the tokens to indicate how important each outcome is to you. You could place all 100 tokens on one outcome if you only care about that outcome. If you feel that all the outcomes are equally important, you will place 20 tokens on each outcome.

_____ Overall quality of life. This includes your physical and emotional well being and how well you can perform your normal daily activities.

_____ Side effects that are caused by the treatment.

_____ Symptoms that are caused by ovarian cancer.

_____ Length of time spent without the cancer growing.

_____ Total length of life remaining.

(To avoid any potential bias introduced associated with the order the concepts are listed, the order will be randomized across participants.)

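### The between-attribute comparison of rank-token correlations in Secondary Aim 4 confounds inconsistency with how concentrated the rankings are and how patients spread their tokens

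*Combined protocol and SAP*

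**What the plan says.** The consistency analysis for Secondary Aim 4 (section 11, Statistical Analysis of Secondary Aims) has three parts.

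- Correlation: the sentence opens with its purpose, "To examine consistency between token allocations with rank preferences, we will reverse order the rank preferences". The full step is to "reverse order the rank preferences such that higher ranks correspond to higher preferences and compute correlation coefficients". This sentence names no unit of analysis.
- Comparison: "We will test whether correlations between ranks and token counts differ between attributes using Spearman rank tests".
- Agreement on the top attribute: "We will also examine the proportion of patients who provided the highest token counts to their most preferred attribute and vice versa".

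The plan also describes mean ranks, the full distribution of ranks, and the mean, SD and median of tokens for each attribute.

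Appendix XI gives the two tasks. In the first, "Please rank the following outcomes we can measure in order from the MOST important (1) to the LEAST important (5) to you". The second begins "Now imagine that you have 100 coins or tokens" and leaves the spread to the patient: "You could place all 100 tokens on one outcome if you only care about that outcome". At the other extreme she may put 20 on each.

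Section 2.7 gives the purpose: "multiple methods of elicitation will be used to assess the robustness of preferences". It calls the work a pilot on whether patient-determined weights for a future composite endpoint are feasible. Under section 7.1, note 14, only Duke patients complete the tasks. Their number is not stated.

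**The concern.** Consistency between two elicitation methods is a within-patient question: do a woman's tokens follow her own ranking over the five attributes? A correlation attached to one attribute asks something else: do women who rank that attribute higher also give it more tokens than other women do?

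Two features can lower that correlation without any inconsistency. Patients spread tokens differently, so 100/0/0/0/0 and 24/22/20/18/16 can accompany the same ranking. And an attribute that most women place first has little variation in rank, so differences in token spread dominate.

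Equal correlations across attributes are therefore not the same as equal consistency across attributes. At stake is the robustness judgement that section 2.7 wants from the pilot: the attribute patients agree on most could look like one of the least consistently valued. Naming a better test of equal correlations would not help, because the difficulty lies in the quantity compared.

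**Working it through.** **Is the statistic across patients?** Each patient supplies one rank and one token count per attribute. A single pair gives no correlation, so a correlation that can differ between attributes must be computed over patients. The documents do not say so, but no other reading of that comparison can be computed.

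**Plan's own figure.** None: Aim 4 has no sample size, alpha or expected correlation. The documents give five attributes, 100 tokens and total accrual of up to 56. Everything else below is assumed.

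**A small example.** Six invented patients whose tokens (each row sums to 100) follow their own ranking exactly:

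| Patient | Quality of life | Side effects | Symptoms | PFS | OS |
|---|---|---|---|---|---|
| 1 | 10 | 5 | 8 | 17 | 60 |
| 2 | 18 | 16 | 17 | 24 | 25 |
| 3 | 21 | 17 | 19 | 20 | 23 |
| 4 | 22 | 18 | 19 | 20 | 21 |
| 5 | 45 | 3 | 7 | 15 | 30 |
| 6 | 26 | 14 | 18 | 19 | 23 |

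The within-patient Spearman correlation is 1 for all six. By attribute it is 0.93 for quality of life, 0.21 for PFS and 0.40 for OS. For side effects and symptoms it is undefined, because every patient gives them the same rank.

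**Large-sample check.** Rankings come from a Plackett-Luce model, in which the chance that an attribute is ranked first is its weight divided by the sum of weights. Token shares come from a symmetric Dirichlet (concentration 1 or 3), sorted and assigned in rank order, so every patient is perfectly consistent. With 40,000 patients, the per-attribute Spearman correlations are:

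| Weights | Ranked first | Favourite | Other four |
|---|---|---|---|
| 1, 1, 1, 1, 1 | 1/5 = 20% each | 0.91-0.92 (all five) | same |
| 10, 1, 1, 1, 1 | 10/14 = 71% | 0.70-0.73 | 0.87-0.89 |
| 3, 1, 1, 1, 1 | 3/7 = 43% | 0.88-0.89 | 0.90-0.91 |

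At 43% the favourite lies about 0.01 to 0.03 below the others. With graded weights 4, 2, 1.5, 1, 0.8 (4/9.3 = 43% first), the highest and lowest correlations differ by about 0.05. The favourite's rank SD is 1.41 under equal popularity, 1.10 at 43% and 0.64 at 71%.

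**How often would a test reject?** The plan does not define its test. The stand-in is a 4-df Wald test on Fisher-z Spearman correlations, bootstrapping whole patients, at nominal 5% (400 trials per setting). The sizes are n = 56 (the maximum) and n = 28 (an assumed half), still with no inconsistent patient:

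- Equal popularity: about 3-10%, the test's own small-sample size.
- 71% favourite: about 42-65% at n = 28 and 69-93% at n = 56.
- 43% favourite, four equal others: about 6-16%, little above that size.

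**The converse.** In a similar model with equal popularity, swapping the tokens of two randomly chosen attributes in 30% of patients lowers all five correlations together, from about 0.91 to about 0.77. A between-attribute comparison then has no difference to find. The mean within-patient correlation falls from 1.00 to 0.84.

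**The case against.** - **The unit is not stated.** The sentence that introduces the correlations could be met by within-patient correlations. This stands: the across-patient reading follows only from the comparison between attributes, and the criticism is confined to that comparison.
- **Stronger readings.** A reader might infer that consistent patients must produce correlations below 1. They need not: if all patients used one identical token-by-rank schedule, all five would equal 1. Appendix XI's free allocation makes that unlikely but does not exclude it. A reader might also infer that the correlations must differ between attributes; that requires unequal rank distributions. Nor does the comparison respond to popularity instead of inconsistency. Inconsistency lowers the correlations, and inconsistency confined to one attribute would move the comparison. The supportable statement is that the two are confounded.
- **The size is assumed.** The documents give no preference distribution, token distribution or number of Duke patients. This stands: the effect is clear under strong consensus and small under mild preference.
- **Partly covered already.** The top-attribute proportion is a within-patient check and, without ties, would be 100% in a perfectly consistent cohort. The planned rank distributions would also show the concentration. Both are real safeguards, but the proportion covers only the first rank, and the plan does not link either to how the correlations are read.
- **Low stakes.** The aim is a pilot, no threshold or decision rests on the test, and section 11.2.2 does not list it among the secondary endpoints. Raw ranks and tokens are kept, so a within-patient measure could be added later. This limits the importance of the point but does not remove it.

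**Conclusion.** The concern holds as one of confounding. Followed as written, the between-attribute test can indicate that attributes differ in consistency when no patient is inconsistent, and it can overlook inconsistency spread evenly over attributes. With an attribute ranked first by about 71%, its correlation is roughly 0.14 to 0.18 below the others (0.87 − 0.73 and 0.89 − 0.70 give 0.14 and 0.19 at the rounded extremes). At about 43% the gap is too small to matter much. These sizes rest on the assumed ranking and token models, and the rejection rates also on a stand-in test. The documents do not show which preference pattern to expect, so they do not support a claim that a false signal is likely in this trial. The consequence is limited to a secondary, Duke-only pilot aim; the primary analysis, response and safety are untouched.

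**What to change.** In Secondary Aim 4, make a within-patient measure over the five attributes the lead consistency summary:

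1. The proportion of patients with no reversed rank-token pair, counting tied tokens as not reversed.
2. The distribution (median and interquartile range) of each patient's Kendall tau-b between reversed ranks and tokens.
3. A separate count of patients who give 20 tokens to every attribute, for whom tau-b is undefined.

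Drop the between-attribute test as a test of consistency. The per-attribute correlations may stay as description, shown beside the rank distributions. Keep the planned top-attribute agreement proportion.

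The cost is one or two sentences and trivial programming, with no new data. The drawback is that tau-b over five items is coarse and lowered by ties. A patient who places all 100 tokens on her first-ranked attribute has 4 concordant, 0 discordant and 6 tied pairs, so tau-b = 4/√(10 × 4) = 0.63 although nothing is reversed. That is why the no-reversal proportion should lead.

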11. See section 7.3 for specimen requirements. Collect whole blood, serum, plasma, and urine pre-cycle #1, every other cycle (i.e. Cycle 3, 5, etc.), at the time of progression, and one month after study treatment is discontinued.
12. Repeat every other cycle and more frequently as clinically indicated. For patients with hepatic injury or elevated liver function tests repeat the INR/PT/PTT every cycle until the liver function tests return to baseline; then resume INR/PT/PTT every other cycle.
13. Repeat every other cycle and more frequently as clinically indicated.
14. Only for subjects enrolled at Duke

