11.0 STATISTICAL CONSIDERATIONS

The primary objective of this study to assess the activity of the study agent as measured by the proportion of patients who survive progression-free for at least 6 months after initiating study therapy in patients with bevacizumab-resistant persistent or recurrent epithelial ovarian, fallopian tube, or primary peritoneal carcinoma.

11.1 The study plan is a single arm, non-randomized, 2-stage phase II clinical trial.

11.2 Parameters employed to evaluate treatment efficacy and toxicity are:

11.2.1 Primary Endpoints:

11.2.1.1 The proportion of patients who survive progression-free for at least 6 months.

11.2.2 Secondary Endpoints:

11.2.2.1 The proportion of patients who have objective tumor response (complete or partial).

11.2.2.2 Frequency and severity of adverse effects as assessed by the active version of the NCI Common Toxicity Criteria.

11.2.2.3 Duration of progression-free survival and overall survival.

11.2.3 Translational Endpoints:

11.2.3.1 To measure baseline levels of VEGF and correlate with treatment outcome.

11.2.3.2 To measure baseline and on treatment levels of additional growth factors (listed in section 2.5) that may be co- or counter- regulated with VEGF and correlate with response to treatment.

11.2.3.3 To measure baseline and on treatment levels of coagulation and endothelial cell activation markers that may predict for thrombotic or bleeding risks related to treatment.

11.3 A total of up to 56 will be accrued at the rate of about 5 patients per month. If the 6-month progression-free survival rate is *observed to be* ≥ 0.20 the trial will be considered a success. Progression-free survival will be defined as the length of time from on-study to disease progression or death, whichever comes first. The study will use a 2-stage optimal design [15] to test the null hypothesis that the 6-month PFS rate is $\leq 13\%$ against the alternative hypothesis that this rate is $\geq 27\%$. The targeted accrual for the first stage will be 27 eligible and evaluable patients but permitted to range from 27 to 31 for PFS determination and administrative reasons. The critical value for the number of patients who survive progression-free for 6 months will be based on the first 27 patients who are both eligible and evaluable for 6 month PFS. An interim analysis will be done after accrual of these patients (Stage 1). After the accrual of these patients, further accrual will be

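### Secondary Aim 4 plans to compare five rank-token correlations but has no valid method: a Spearman test asks only whether one correlation is zero

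*Combined protocol and SAP*

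**What the plan says.** Secondary Aim 4, in section 11.3 under the analysis of secondary aims, has two steps for agreement between the ranking and token exercises. First, "we will reverse order the rank preferences such that higher ranks correspond to higher preferences and compute correlation coefficients"; the type of coefficient is not given. Then: "We will test whether correlations between ranks and token counts differ between attributes using Spearman rank tests".

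The data come from Appendix XI. Part B instructs the patient: "Please rank the following outcomes we can measure in order from the MOST important (1) to the LEAST important (5) to you". Part C begins "Now imagine that you have 100 coins or tokens" and adds: "If you feel that all the outcomes are equally important, you will place 20 tokens on each outcome".

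Note 14 to the table in section 7.1 limits these tasks: "Only for subjects enrolled at Duke". The number of Duke patients is not stated. Section 11.3 caps the whole trial: "A total of up to 56 will be accrued at the rate of about 5 patients per month". Section 2.7 describes the preference work as a pilot in which "multiple methods of elicitation will be used to assess the robustness of preferences".

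For this comparison the documents state no null hypothesis, significance level, sample size or treatment of within-patient dependence, and no other section names a method for comparing correlations.

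**The concern.** The question concerns differences among five correlations. The only test named concerns whether a single correlation is zero, so an analyst following the sentence literally would obtain five p-values that do not address it. Similar coefficients can give different verdicts, and very different coefficients can give the same one.

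At stake is any statement that patients are consistent across elicitation methods for one outcome but not another, or equally consistent for all. Section 2.7 wants to know whether patient-determined weights are feasible for a future composite endpoint, and agreement by outcome bears on that. Such a statement would have no support from the analysis as written.

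**Working it through.** There is no stated figure to reproduce: Aim 4 gives no sample size, significance level or power.

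**1. What the named test tests.** For one attribute with N patients, using the usual t approximation,

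t = r × √((N − 2)/(1 − r²)) on N − 2 degrees of freedom,

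with null hypothesis ρ = 0. The critical coefficient is r = t₀.₉₇₅ / √(N − 2 + t₀.₉₇₅²). No second correlation enters either formula.

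**2. Critical values.** Two-sided 0.05 and the values of N are assumptions; 56 is the ceiling from section 11.3. For N = 30, r = 2.048/√(28 + 2.048²) = 0.361. For N = 20 and N = 56 the values are 0.444 and 0.263.

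**3. What separate p-values would show.**

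| N | r | p | Against 0.05 |
|---|---|---|---|
| 30 | 0.37 | 0.044 | significant |
| 30 | 0.36 | 0.051 | not significant |
| 30 | 0.40 | 0.029 | significant |
| 30 | 0.90 | < 0.001 | significant |

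For example, 0.37 × √(28/(1 − 0.37²)) = 2.107 exceeds 2.048, and 0.36 × √(28/(1 − 0.36²)) = 2.042 does not. A difference of 0.01 splits the verdict; a difference of 0.50 does not.

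**4. Simulated preference data** (600 runs; five attributes, ranks 1 to 5, 100 tokens; noise levels assumed).

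| Truth | N | All five tests significant |
|---|---|---|
| Equal, about 0.77 | 15 | 78% |
| Equal, about 0.78 | 30 and 56 | 100% |
| Four about 0.81, one 0.57 | 15 | 62% |
| Four about 0.82, one 0.59 | 30 | 95% |
| Four about 0.83, one 0.59 | 56 | 99.8% |

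At N = 30 and above the result is almost the same whether or not the correlations differ. At N = 15, 100 − 78 = 22% of runs with equal correlations give a result other than all five significant.

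**5. Dependence.** Each patient supplies all five ranks, which always sum to 1 + 2 + 3 + 4 + 5 = 15, and all five token counts, which sum to 100. A test for correlations from independent samples would therefore also be unsuitable.

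**6. Check of the replacement intervals.** The inputs are illustrative: five latent utilities per patient (SD 1), with ranks and tokens from separate noisy copies (noise SD 0.7); 1,500 runs of 399 patient-level resamples. Coverage of 95% percentile intervals at N = 20, 30 and 56 was 93–96% with equal average importance and 93–95% with mild differences. With strong differences (utility means 2.5, 1, 0, 0, −1.5) it was 89–93%, 93–95% and 92–95%.

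Below N = 20, two smaller reruns of the strong case, with a softmax token split assumed, gave worst-attribute coverage of 76% and 81% at N = 15, and 71% and 73% at N = 12. Both gave about 89% at N = 20. Mean interval width at N = 20, 30 and 56 was 0.65, 0.52 and 0.37 (equal) and 0.72, 0.60 and 0.44 (strong).

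In the strong case true correlations ranged from 0.35 to 0.51 with identical noise for every attribute, so the differences arose from restricted range alone.

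**7. An equality test that respects dependence.** A patient-level bootstrap Wald test on Fisher-z values (150 runs, model of step 4) rejected equal correlations in 11% of runs at N = 30 and 7% at N = 56, and unequal ones in 54% and 83%. It responds to a difference, but its type I error is too high at N = 30.

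**The case against.** The fairest defence is that Spearman names the coefficient. The preceding sentence leaves its type open, and this one may supply it. A reader might infer that the plan commits to five tests against zero and to reading differences from the pattern of significance. The documents do not say that: they give no null hypothesis and no rule for interpreting a set of p-values. This defence stands as far as it goes. It changes the defect from a wrong test to an absent one, and the comparison still cannot be run from the text.

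Second, the pair 0.37 and 0.36 was chosen to straddle the critical value. Two exercises completed by the same patient on the same five outcomes may well correlate more strongly, and then a split verdict would be rare at N = 30 or more. This also stands: the examples show what the test can and cannot do and are not forecasts. With strong correlations the tests are uninformative about differences, as step 4 shows.

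Third, little depends on the comparison. The rest of Aim 4 is largely descriptive, no decision rule uses the result, and the proportion giving most tokens to their top-ranked outcome already addresses consistency. This limits the priority of the point but does not supply the missing method.

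Finally, the protocol asks for a between-attribute comparison, and a descriptive replacement abandons it. That is a fair criticism, so the fix offers a way to keep it.

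**Conclusion.** The plan has no valid method for comparing rank-token correlations between attributes, on either reading of the sentence. This rests on the null hypothesis of the Spearman test and on the shared patients in Appendix XI, not on the simulations, whose sample sizes, noise levels and significance level are assumptions.

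The size is small: one exploratory comparison in a Duke-only pilot. A reader might infer that the preference analysis as a whole is unsound. The documents do not support that: the coefficients, the top-choice agreement proportion, and the rank, token and concern summaries can all be produced as written. The primary endpoint, two-stage rule and safety analyses do not draw on this comparison. It is a desirable clarification, not a required correction.

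**What to change.** Replace the sentence with:

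> For each attribute the Spearman correlation between reversed rank and token count will be reported descriptively, with a 95% percentile interval from a bootstrap resampling whole patients if at least 20 Duke patients contribute, and without an interval otherwise. Undefined resamples will be excluded and counted, and an undefined observed coefficient will be reported as not estimable. No inference about differences between attributes will be drawn from per-attribute p-values.

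If the sponsor wants to keep the comparison, it should instead name, before any preference data are seen, one exploratory equality test for dependent correlations based on patient-level resampling. Its type I error should be checked at the expected Duke N, and the plan should note that unequal correlations may reflect restricted range alone when nearly all patients rank an attribute alike.

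The cost is one sentence and a short program, with no new data. The downside is that the between-attribute comparison is dropped or only weakly tested. The intervals are wide and, even at the threshold of 20, may cover only about 89% for an attribute that patients rank almost alike. The threshold matters because stage 1 of this multi-center trial has 27 to 31 patients and accrual may end there, so fewer than 20 Duke patients is possible.
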